## Research Design

	Observational Research		Experimental Research					
Descriptive Research	Yes 							Retrospective Research
		Yes 						
		Yes X						
Analytical Research	Yes 							Retrospective Research
		Yes 						
		Yes 						
Controlled Research			Yes 					Blind Research
			Yes 					Double-blind Research
			Yes 					Open Research
				Yes 				
					Yes 			
						Yes 		
Uncontrolled Research						Yes 	Yes 	
	Cross Sectional Research	Longitudinal Research	Randomized Controlled Research	Non-Randomized Controlled Research	Cross-Randomization	Before and After Research		

## PROCESS

What are the damages, risks and process problems that can be encountered during the research?	NO
What are the measures that can be taken against them?	NO

## SAMPLE INFORMATION

How was the number of volunteers to participate in the research determined? Explain	When calculating the sample size of our study, reference values in previous similar studies were taken into consideration. When similar dental studies are examined; ( $\mu_1 - \mu_2$ ) and sd values are seen to range from 0.01 to 0.05 (Odacı E. v.d, 2003). When determining the sample size of the study ( $\alpha=0,05$ , $1-\beta=80\%$ ) $f(\alpha, \beta)=7,85$ , $sd =0,05$ and ( $\mu_1 - \mu_2$ ) = 0,02 when taken, it is seen that the sample size is $n = 100$ . It is planned to include 100 volunteers in our research.
Sampling method	Volunteers will be selected from patients who applied to our clinic and who have complaints of temporomandibular joints.

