1. Klatkiewicz, T., et al., Ultrasonography in the Diagnosis of Temporomandibular Disorders: A Meta-Analysis. Med Sci Monit, 2018. 24: p. 812-817.
2. Su, N., et al., Diagnostic value of ultrasonography for the detection of disc displacements in the temporomandibular joint: a systematic review and meta-analysis. Clin Oral Investig, 2018. 22(7): p. 2599-2614.
3. Melis, M., S. Secci, and C. Ceneviz, Use of ultrasonography for the diagnosis of temporomandibular joint disorders: a review. Am J Dent, 2007. 20(2): p. 73-8.

**PURPOSE OF THE RESEARCH** In the literature, there are not many studies on the diagnostic value of the use of ultrasonography in the diagnosis of temporomandibular joint diseases in dentistry. In this study, it is aimed to contribute to the literature in terms of revealing the reliability of the use of ultrasonography in the diagnosis of temporomandibular joint diseases.

**BENEFITS EXPECTED AT THE END OF THE RESEARCH** By revealing the efficacy and reliability of ultrasonography in the diagnosis of temporomandibular joint diseases, to eliminate the disadvantages of MR and other imaging methods.

**RESEARCH METHOD** Functional joint examination and ultrasonographic examination (USG) will be applied to all volunteers who will participate in the research. In the USG application, when the mouth is open and closed, the right and left joint intervals will be measured and a note will be taken. At the same time, right and left masseter muscle thicknesses will be measured separately at free-closing and tight-closing and a grade will be taken for all groups..

Volunteers to participate in the research will be divided into 4 groups.(I,II,III,IV).For volunteers in group 1 with previously taken MR images, USG and MR findings will be compared. In volunteers in group 2, the values obtained using different probes (linear, hockeystick) will be compared. In the third group of volunteers, the values to be obtained by using the USG probe at different angles (horizontal / longitudinal) will be compared. In volunteers in group 4, the megahertz values of the probe are changed and the findings obtained by examining them separately will be compared.

In addition to evaluating 4 groups separately, at the end of the research, USG data applied to all 4 groups will be

Protocol Information Form for Clinical Research	Doc. Code	Rev. Date/ No:	Page
	Form 3	13.06.2013/ÜDHFKA EK 00	2/6

analyzed by comparing all the findings obtained in functional joint examination.

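### The 80% power behind n = 100 rests on a difference and SD tied to no measurement, unit or planned comparison, and is not shown for any comparison the study will make

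*Combined protocol and SAP*

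**What the plan says.** The only justification of size is in the protocol's SAMPLE INFORMATION section. It reports that "reference values in previous similar studies were taken into consideration" and gives a single range for both inputs: mean differences and "sd values are seen to range from 0.01 to 0.05". It then fixes alpha at 0.05, power at 80%, the multiplier f at 7.85, the SD at 0.05 and the difference at 0.02, and arrives at n = 100. That figure becomes the study total: "It is planned to include 100 volunteers in our research".

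The RESEARCH METHOD section describes what will be measured: "when the mouth is open and closed, the right and left joint intervals will be measured and a note will be taken". Masseter thickness is also measured on both sides, at free and at tight closing. The same section states: "Volunteers to participate in the research will be divided into 4 groups". Each group has its own comparison: ultrasound against existing MR images, two probes, two probe angles, and different probe frequencies. One further analysis sets the ultrasound data of all groups against the functional examination. No group sizes are given, and no measurement or comparison is named as primary.

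The section on statistical methods lists chi-square, Student's t and Mann-Whitney tests between groups. It does not say which comparison the 80% belongs to.

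**The concern.** A power figure belongs to one measurement, one comparison and one design. Here the two numbers that produce it have no unit and are not linked to joint interval, masseter thickness or anything else the study records. It is also not said whether 0.05 is the spread between people or the spread of paired differences. For method comparisons made within the same volunteers, that distinction decides the answer.

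The study aims to show reliability but plans tests of difference. A non-significant difference between probes, angles or ultrasound and MR could be taken as agreement, and a stated 80% power would make that look safer than the design supports.

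**Working it through.** **Inputs from SAMPLE INFORMATION:** alpha 0.05, power 80%, f = 7.85, SD 0.05, difference 0.02, quoted range 0.01 to 0.05 for both, total 100. **From RESEARCH METHOD:** four groups, with method comparisons inside each. **Assumptions:** 25 per group (equal split); within-person correlation between 0 and 0.8.

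**1. Reproduce the plan's figure.**
- f = (1.960 + 0.842)² = 7.85, so the test is two-sided. One-sided, f would be 6.18.
- Two independent means: n per group = 2 × f × (SD/difference)² = 2 × 7.85 × (0.05/0.02)² = 98.1, which rounds up to 99. An exact t test gives 99.1. The stated 100 agrees.
- Alternatives that do not give 100: one-sided, 78 per group; paired with SD of differences 0.05, 7.85 × 6.25 = 49.1; total for two groups, 2 × 99 = 198.
- A paired design with between-person SD 0.05 and zero within-person correlation has the same formula and needs 100 pairs. That would take all 100 volunteers in one method comparison and no correlation between two readings of the same joint.

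**2. Sensitivity to the plan's own range, with SD held at 0.05.**

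| Difference | 2 × 7.85 × (0.05/difference)² | n per group |
|---|---|---|
| 0.01 | 392.5 | 393 |
| 0.02 | 98.1 | 99 |
| 0.03 | 43.6 | 44 |
| 0.04 | 24.5 | 25 |
| 0.05 | 15.7 | 16 |

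The span is 25-fold. With 100 in each of two groups, t-test power would be 29% at 0.01, 80% at 0.02 and above 99.9% at 0.05.

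**3. Power for the comparisons that are planned** (difference 0.02, paired t test).
- If 0.05 is the SD of paired differences, the effect is 0.02/0.05 = 0.4. Power is 48% with 25 volunteers and 98% with 100. Because group sizes are not stated, a range helps: 30% with 15 and 69% with 40. About 51 are needed for 80%. Since 2 × 51 = 102 exceeds 100, at most one of the four groups could be that large.
- If 0.05 is a between-person SD, the SD of differences is 0.05 × √(2(1 − ρ)). With 25 volunteers:

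| ρ | SD of differences | Effect | Power |
|---|---|---|---|
| 0 | 0.0707 | 0.283 | 27% |
| 0.5 | 0.0500 | 0.400 | 48% |
| 0.8 | 0.0316 | 0.632 | 86% |

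- If a comparison of two independent subsets was meant, 50 against 50 gives 51% and 25 against 25 gives 28%.

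**4. What a group of 25 can deliver**, in units of the SD of paired differences (t on 24 degrees of freedom = 2.064).
- 95% interval for the mean difference: ±2.064/√25 = ±0.41.
- 95% interval for each limit of agreement: ±2.064 × √(1/25 + 1.96²/(2 × 24)) = ±0.72.
- Detectable difference at 80% power, paired t test: 0.58. The normal approximation √(7.85/25) gives 0.56.

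**The case against.** The strongest reply is that the formula uses only the ratio 0.02/0.05 = 0.4, which has no unit. The paragraph then reads coherently as 80% power for a 0.4 SD difference with about 100 per group, and the arithmetic is right. This stands. A reader might infer that without units the power statement is meaningless, neither true nor false; that goes too far. What remains open is why 0.4 SD is the relevant effect, for which measurement, and in which comparison 100 per group occurs.

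The plan also chose the top of its quoted SD range, which is the cautious end. For that reason the sensitivity above holds the SD at 0.05. Letting both inputs vary would stretch the span to 1 to 393 per group, but the low end is 0.63 rounded up, from an extreme corner of the range, and is not a usable sample size.

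Two further inferences are tempting and unsupported:
- That 0.02 is too small for ultrasound to resolve. The documents give neither a unit nor the probe frequencies, and a mean difference can be estimated more finely than a single reading.
- That the 2003 source is suspect because it is missing from the reference list. That list serves the rationale, the source is cited where it is used, and its content cannot be judged from these documents.

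Finally, the study is marked as descriptive, so misreading of a null result is a risk and not a certainty.

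**Conclusion.** The concern holds. The plan's n = 100 follows from its inputs as a per-group number for two independent means. The planned method comparisons are within volunteers, inside four groups that share 100. No planned comparison with identified inputs comes out at 80%.

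On the plan's own difference and SD, a group of 25 has between 27% and 86% power, depending on what the SD represents and on a correlation the documents do not give. It has 48% if 0.05 is the SD of paired differences. These figures assume an equal split.

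This does not show that every comparison is underpowered. With high within-person correlation, 25 volunteers would exceed 80%. The 80% is unsupported, which is different from being shown false. Nor is it only a matter of how 100 is divided: with 100 in every group, the inputs would still belong to no named measurement.

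**What to change.** Rewrite the sample-size paragraph:
- Delete the 80% claim.
- Name one measurement in mm, for example the closed-mouth joint interval, and one paired comparison within one group.
- State that group's size and the precision it gives. With 25 volunteers (if the split is equal), use the step 4 figures: ±0.41 SD of the paired differences for the mean difference, ±0.72 SD for each 95% limit of agreement, and a detectable difference of 0.58 SD at 80% power. Recompute them if the group size differs.
- Take any SD estimate from paired differences of that same comparison. Early enrolees spread over four different comparisons would not supply it.
- Do not quote agreement precision for n = 100, because no method comparison is planned in all 100 volunteers.

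The cost is one paragraph and a less favourable stated figure. No additional volunteers are needed.

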## VOLUNTEER POPULATION INFORMATION

Volunteers' inclusion criteria	-Patients over the age of 18 who apply with TMJ problems -Patients with pain in the joint and chewing muscle area
Volunteers' criteria for exclusion from research	-Syndromic patients -Patients under the age of 18 -Patients with a history of orthognathic surgery -Pregnants -Antidepressant Users -Patients Using Removable Dentures -Patients who have had joint treatment in the past six months

Age range	
	Child Age Group (0-17) Number:0
	Over 18 years old Number:100
	Total:100
Sex	
	Female
	Male
	Total: 100

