**WHICH STATISTICAL METHODS WILL BE EVALUATED**

In our study, SPSS application will be used for statistical analysis.

In evaluating the categorical variables, the Chi-Square test will be used to look for a difference between the groups. Normality control of continuous variables will be done with Kolmogorov-Smirnov test.

Difference evaluations of continuous variables between groups will be made with Student's t test in data with normal distribution. Group comparisons for data that are not suitable for normal distribution will be performed with Mann Whitney U test.

Descriptive statistics will be specified by giving mean, standard deviation, minimum and maximum values of all continuous variables. Frequency distributions and percentages of categorical variables will be specified.

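### The sample size of 100 is a per-arm (or per-comparison) figure used as the total for four separately evaluated groups, so 80% power is not supported for the group comparisons

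*Combined protocol and SAP*

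**What the plan says.** The SAMPLE INFORMATION section gives alpha 0.05, power 80%, a multiplier f of 7.85, sd 0.05 and a difference of 0.02, and states a result of n = 100. No formula is printed. It adds that, in similar dental studies, the difference and "sd values are seen to range from 0.01 to 0.05". The section ends: "It is planned to include 100 volunteers in our research". VOLUNTEER POPULATION INFORMATION repeats this as the whole study: "Over 18 years old Number:100".

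Under RESEARCH METHOD, "Volunteers to participate in the research will be divided into 4 groups". Group 1 compares ultrasound with existing MR images, group 2 two probes, group 3 two probe angles, and group 4 probe frequencies. For group 2, for example: "In volunteers in group 2, the values obtained using different probes (linear, hockeystick) will be compared". The groups are evaluated one by one, with a further pooled analysis against the functional examination: "In addition to evaluating 4 groups separately, at the end of the research, USG data applied to all 4 groups will be" analysed together. Some measurements are taken in everyone: "right and left masseter muscle thicknesses will be measured separately at free-closing and tight-closing and a grade will be taken for all groups".

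The statistical methods section names one parametric test for continuous data: "Difference evaluations of continuous variables between groups will be made with Student's t test in data with normal distribution". It names no paired test.

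**The concern.** A sample size formula returns the number needed for one comparison, either in each arm or in pairs. Here that number becomes the total for a study of four groups with four separate questions. Four groups sharing 100 volunteers cannot each hold 100.

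The SAMPLE INFORMATION paragraph is the only justification for enrolling 100, and the group comparisons are the structure of the study. A reader will naturally take the 80% to apply to them. The aim is to show that ultrasound is reliable, so a non-significant difference between probes, angles or modalities may be read as agreement. If that reading leans on 80% power that was never shown for the group, it is unsafe.

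**Working it through.** **Inputs.** From SAMPLE INFORMATION: alpha 0.05, power 80%, f = 7.85, sd = 0.05, difference = 0.02, total 100. From RESEARCH METHOD: four groups, sizes not stated. Within-volunteer correlations (rho) below are assumptions.

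**Step 1: the multiplier.** (1.960 + 0.842)^2 = 7.85, so f is correct for two-sided 5% and 80% power.

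**Step 2: reproduce n = 100.**
- Two independent arms: 2 × 7.85 × 0.05^2 / 0.02^2 = 98.1 *per arm*, about 200 in all. By the noncentral t distribution, 100 against 100 gives 80.4%.
- Pairs, with 0.05 the SD of a single measurement and rho = 0: the variance of the difference is 2 × 0.05^2, which again gives 98.1. With 100 pairs the power is 79.98%.
- Pairs, with 0.05 the SD of the differences: 7.85 × 0.05^2 / 0.02^2 = 49.1. This does not give 100.

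The figure reproduces as a per-arm size or as the pairs in one comparison at zero correlation. On neither reading is it a total for four comparisons.

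**Step 3: what a group can hold.** 100 / 4 = 25. An equal split gives 25 each; any unequal split leaves at least one group smaller.

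**Step 4: power at the plan's sd and difference** (noncentral t, two-sided 0.05).

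Independent volunteers: 25 v 25 gives 28%. The best that 100 volunteers allow, 50 v 50, gives 51%.

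Two readings per volunteer, with SD of differences = 0.05 × sqrt(2(1 − rho)):

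| rho | SD of differences | 25 pairs, paired t | 100 pairs, paired t |
|---|---|---|---|
| 0 | 0.071 | 27% | 80% |
| 0.25 | 0.061 | 35% | 90% |
| 0.5 | 0.050 | 48% | 98% |
| 0.75 | 0.035 | 77% | >99% |
| 0.77 | 0.034 | 81% | >99% |
| 0.9 | 0.022 | 99% | >99% |

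With 25 pairs, 80% power needs an SD of differences of about 0.034 or less, which is rho of about 0.77 at sd 0.05.

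**Step 5: other values inside the plan's 0.01 to 0.05 range.** With 25 pairs and a single-measurement sd of 0.03, a difference of 0.02 has 62% power at rho 0 and 89% at rho 0.5. A difference of 0.01 has 20% and 36%.

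**Secondary: the test as written.** If the independent t test were applied to the two readings of the same 25 volunteers (sd 0.05, difference 0.02), simulated power would be 28%, 26%, 22%, 15% and 8% at rho 0, 0.25, 0.5, 0.75 and 0.9. The fall with rising correlation comes from the choice of test, not from the sample size.

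**The case against.** **The paragraph never assigns the 80% to the four groups.** This is true. One within-volunteer comparison over all 100, such as masseter thickness at free and tight closing, would have 80% power or more. But the plan does not name such a comparison as the target, and no other sample size argument is offered for the groups.

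**The group comparisons are within-volunteer, so correlation may rescue them.** It may, as the table shows. This limits the conclusion to *not supported*; *underpowered* would go too far. The plan gives no correlation or SD of differences and names no paired test, so the rescue is not demonstrated.

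**The lowest figures come from the wrong test.** This is fair, and they are marked as secondary. The conclusion does not need them.

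**Groups 1 and 4 may not be two-reading comparisons of means.** The plan speaks of findings there, which may be categorical, and does not say how many frequencies group 4 uses. The paired figures apply most directly to groups 2 and 3. The limit of 25 in the smallest group applies whatever the endpoint.

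**Both joints are measured.** Taking 50 joint pairs per group at sd 0.05 and rho 0.5 would give about 79% if the two sides' differences were independent, which is a best case. The plan does not say that the joint is the unit.

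**The study is marked descriptive, and the arithmetic is right.** Both are so. The plan still states alpha and power and plans hypothesis tests; the fault is in how a correct number is applied.

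**Conclusion.** The concern holds. The calculation is right for one comparison and is misapplied as the total for four. For the group comparisons the stated 80% is not supported: at the plan's sd and difference, a group of 25 has 28% power for two independent sets of 25, and between 27% and 99% for pairs, depending on a correlation that the plan does not give. No split of the 100 into two independent sets exceeds 51%.

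The 25 per group is an assumption, but it is the most the smallest of four groups can have. The correlations are also assumed. The conclusion does not extend to a single within-volunteer comparison over all 100, which would reach 80% or more. The paragraph must be corrected, because it is the sole basis for the enrolment figure.

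**What to change.** Rewrite the SAMPLE INFORMATION paragraph so that it:

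1. says what 98 to 100 is the size of, and which comparison it serves. If that is one within-volunteer comparison over all volunteers, name it and keep the 80% for that comparison only;
2. states that the 80% does not apply to the four group comparisons;
3. gives each group's planned size, whether its comparison is paired, whether the unit is the volunteer or the joint, and the SD of within-volunteer differences assumed;
4. restates power or detectable difference for those sizes as a range.

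For 25 pairs, the range would be:

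| SD of differences | Detectable difference at 80% power | 95% CI half-width |
|---|---|---|
| 0.071 | 0.041 | 0.029 |
| 0.050 | 0.029 | 0.021 |
| 0.034 | 0.020 | 0.014 |
| 0.022 | 0.013 | 0.009 |

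Report the group comparisons as estimates with confidence intervals, so that a non-significant result is not read as agreement.

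The cost is one reworded paragraph and the group sizes. No extra volunteers or procedures are needed, provided the group comparisons are presented as estimates. The downside is a less favourable stated power for them.

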## VOLUNTEER POPULATION INFORMATION

Volunteers' inclusion criteria	-Patients over the age of 18 who apply with TMJ problems -Patients with pain in the joint and chewing muscle area
Volunteers' criteria for exclusion from research	-Syndromic patients -Patients under the age of 18 -Patients with a history of orthognathic surgery -Pregnants -Antidepressant Users -Patients Using Removable Dentures -Patients who have had joint treatment in the past six months

Age range	
	Child Age Group (0-17) Number:0
	Over 18 years old Number:100
	Total:100
Sex	
	Female
	Male
	Total: 100

## WHAT ARE THE DATA TOOLS USED IN THE RESEARCH?

With the Information-Questionnaire	
	 Self-answer
	 Answering under observation
	 Answering through the interviewer
	Observation
	Laboratory Review
	Registration from the archive
	Other

Protocol Information Form for Clinical Research	Doc. Code	Rev. Date/ No:	Page
	Form 3	13.06.2013/İÜDHFKA EK 00	4/6

**WHICH STATISTICAL METHODS WILL BE EVALUATED**

In our study, SPSS application will be used for statistical analysis.

In evaluating the categorical variables, the Chi-Square test will be used to look for a difference between the groups. Normality control of continuous variables will be done with Kolmogorov-Smirnov test.

Difference evaluations of continuous variables between groups will be made with Student's t test in data with normal distribution. Group comparisons for data that are not suitable for normal distribution will be performed with Mann Whitney U test.

Descriptive statistics will be specified by giving mean, standard deviation, minimum and maximum values of all continuous variables. Frequency distributions and percentages of categorical variables will be specified.

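### The four group comparisons are made within the same volunteers, but the plan names only tests for separate groups and no paired or repeated-measures method

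*Combined protocol and SAP*

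**What the plan says.** The Research Method section of the combined protocol and SAP gives each group its own comparison:

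- Group 1: "For volunteers in group 1 with previously taken MR images, USG and MR findings will be compared".
- Group 2: "In volunteers in group 2, the values obtained using different probes (linear, hockeystick) will be compared".
- Group 3: readings obtained by "using the USG probe at different angles (horizontal / longitudinal) will be compared".
- Group 4: "In volunteers in group 4, the megahertz values of the probe are changed and the findings obtained by examining them separately will be compared".

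These are planned analyses in their own right. The pooled comparison with the functional examination comes on top of them: "In addition to evaluating 4 groups separately, at the end of the research".

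The section headed Which Statistical Methods Will Be Evaluated is the only statistical methods text. For continuous data it says "Difference evaluations of continuous variables between groups will be made with Student's t test in data with normal distribution" and "Group comparisons for data that are not suitable for normal distribution will be performed with Mann Whitney U test". For categorical data, "the Chi-Square test will be used to look for a difference between the groups". The rest is a Kolmogorov-Smirnov normality check and descriptive statistics.

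**The concern.** In every group the same volunteers supply both (or all) sides of the comparison. Nothing in the text splits a group into different people per probe, angle or frequency. The named tests are for comparing different people. At the least, then, the comparison that defines each group has no suitable test specified.

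That the tests would be run in their independent form is an inference, but a strong one. The t-test is tied to differences between groups, and its non-normal partner is Mann-Whitney U, which goes with the independent-samples t-test. In that form the standard error ignores the correlation between two readings on one person. When that correlation is positive, as can be expected for two readings of the same joint, the test is too conservative. A real effect of probe, angle, frequency or modality is then missed more often than the data require, and a non-significant result can be misread as showing that the techniques are interchangeable.

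If group 4 uses three or more frequencies, which the plan does not state, no two-sample test fits at all.

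**Working it through.** **Inputs from the plan (Sample Information).** Alpha 0.05, power 80%, f(α, β) = 7.85, SD 0.05, difference 0.02, 100 volunteers. Research Method: four groups, sizes not given.

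**Assumptions not in the plan.** 25 volunteers per group (100/4); a correlation ρ between the two readings; and the plan's 0.02 and 0.05 applied to each group's comparison.

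**Step 1: the plan's own figure.** For two independent means, n per arm = 2 × SD² × f / difference² = 2 × 0.05² × 7.85 / 0.02² = 98.1, so 99 per arm, close to the stated 100. The one-sample or paired form, f × SD² / difference², gives 49.1. The stated 100 therefore fits an unpaired calculation, although the plan uses it as the total.

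**Step 2: what pairing changes.** The SD of the within-volunteer difference is 0.05 × √(2(1 − ρ)). At ρ = 0.5 this is 0.05, so with 25 pairs the true standard error is 0.05/√25 = 0.0100. The independent test assumes 0.05 × √(2/25) = 0.0141. By normal approximation:

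- Type I error of the independent test: 2 × (1 − Φ(1.96 × 0.0141/0.0100)) = 0.56%, not 5%.
- Power of the independent test: 1 − Φ((1.96 × 0.0141 − 0.02)/0.0100) = 22%.
- Power of the paired test: Φ(0.02/0.0100 − 1.96) = 52% (48% with the exact noncentral t).

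**Step 3: results over ρ.** Simulation with 40,000 trials per setting, bivariate normal data, two-sided 5%, n = 25:

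| ρ | Independent t, power | Paired t, power | Independent t, true type I error |
|---|---|---|---|
| 0 | 28% | 27% | 5.2% |
| 0.3 | 25% | 37% | 2.0% |
| 0.5 | 22% | 48% | 0.7% |
| 0.7 | 17% | 70% | 0.1% |
| 0.8 | 13% | 86% | below 0.1% |

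Mann-Whitney U against Wilcoxon signed-rank (5,000 trials) shows the same pattern: 22% vs 34%, 19% vs 46% and 16% vs 69% at ρ = 0.3, 0.5 and 0.7.

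**Step 4: sensitivity (independent vs paired t).**

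- Group size 15: 15% vs 23%, 11% vs 30%, 7% vs 46% at ρ = 0.3, 0.5, 0.7.
- Group size 40: 41% vs 55%, 39% vs 69%, 37% vs 89% at the same ρ.
- Difference, within the plan's range of 0.01 to 0.05 (n = 25, SD 0.05, ρ = 0.5): 4% vs 16% at 0.01; 98% vs about 100% at 0.05.
- SD, for which the plan gives the same range (n = 25, difference 0.02, ρ = 0.5): 38% vs 66% at 0.04; 69% vs 89% at 0.03; 98% vs 99.8% at 0.02.

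**Step 5: binary findings.** The plan gives no proportions, so this is illustration only (50% vs 70% positive, n = 25). Chi-square against McNemar exact / mid-p: 30% vs 26% / 36% at a correlation of 0.3; 27% vs 33% / 46% at 0.5. Chi-square's true type I error at 50% vs 50% is 2.8% and 0.9%.

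**Step 6: pairs needed.** With the plan's inputs, the smallest number of pairs giving the paired t-test at least 80% power is 71, 52, 32 or 22 at ρ = 0.3, 0.5, 0.7 or 0.8. With 25 pairs, 80% is reached only from ρ of about 0.77.

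**The case against.** - **Student's t could include the paired form.** Possible, but the text ties it to differences between groups. Even if granted, Mann-Whitney U and Chi-square remain unsuitable for paired data.
- **The section may be meant only for the pooled functional-examination analysis.** The named tests may suit comparisons between different volunteers there. The four group comparisons would then have no test at all, which is the minimum form of the concern.
- **The sample size is weak evidence of intent.** Fair: no formula is printed, and 100 matches only as a per-arm figure while the plan uses it as a total. It supports the reading but does not carry it.
- **The size is conditional, and SD 0.05 is the top of the plan's range.** This stands. The loss shrinks quickly at a smaller SD, as step 4 shows. But 0.02 and 0.05 are the plan's own choice.
- **The error is conservative.** True under positive correlation: it does not create false differences. It does hide real ones, in a study that asks whether the technique changes the reading.
- **The binary case is unanchored.** This stands. No binary finding is defined for these comparisons, and exact McNemar has less power than Chi-square at the lower correlation.
- **Paired tests do not measure reliability.** Also true. Agreement needs its own analysis, so the correction is necessary but not sufficient for the study's aim.

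**Conclusion.** The concern holds and should be fixed before the data are analysed. The plan sets up within-volunteer comparisons in all four groups and names no method for them. With an assumed 25 volunteers per group and the plan's inputs, the independent t-test keeps less than half of the paired test's power at ρ of 0.5 and above. There is no loss at ρ near zero and little when the difference is large relative to the SD.

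The mismatch itself needs no assumption. Its size rests on the assumed ρ, group size and carry-over of 0.02 and 0.05 to each comparison. The plan ranks no endpoint, so the finding concerns the comparison it gives to each group. It does not cover comparisons between different volunteers in the pooled analysis. Nor does it cover open/closed mouth, free/tight closing or right/left, which are measured but not announced as tests.

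**What to change.** In the statistical methods section, for the comparisons in groups 1 to 4 (and for open/closed, free/tight or right/left if these are tested):

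- Use the paired t-test, or Wilcoxon signed-rank if the paired differences are not normal. Check normality on the differences.
- Use McNemar's test for paired binary findings, stating whether it is the exact or mid-p form.
- Use a repeated-measures or mixed model, or Friedman's test for non-normal data, if group 4 has three or more frequencies.
- Average right and left per volunteer, or include a volunteer random effect. This is a caution for the correction, not a defect in the plan: a paired t-test counting 50 joints from 25 volunteers as independent would have type I error of 8.7%, 11.1% or 13.7% at a side-to-side correlation of the differences of 0.3, 0.5 or 0.7, against about 5% with sides averaged.
- Keep Student's t, Mann-Whitney U and Chi-square for comparisons between different volunteers.

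In Sample Information, restate the basis for paired data, with the assumed correlation and the number of pairs per comparison (step 6).

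The cost is a change of text, a restated sample-size basis and slightly more analysis work for the two sides; no new measurements are needed. The change does not by itself secure power, and agreement still needs a separate analysis.
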